5.5.5.2. University of California, San Diego Shortness of Breath Questionnaire (UCSD)

The UCSD is a 24-item assessment of breathlessness associated with various activities of daily living. The response for each item is measured on a 5-point Likert scale from 0 (none at all) to 5 (maximal or unable to perform). Paper questionnaires will be provided to sites prior to subject enrollment.

5.5.5.3. Borg Dyspnea Scale

The Borg Dyspnea scale is a 1-item assessment, self-administered by the patient administered as part of the 6 MWT. The instrument will be used to assess dyspnea from the patient's perspective. The Scale ranges from 0 (Nothing at all) to 10 (Absolute maximum/Highest possible). Refer to the Procedure Manual for a copy of the assessment. A paper scale will be provided to sites prior to subject enrollment.

5.5.5.4. A Tool to Assess Quality of Life (ATAQ) in IPF

ATAQ questionnaires will be administered in Part B of this study. Paper questionnaires will be provided to sites prior to subject enrollment in Part B of the trial.

5.5.5.4.1. A Tool to Assess Quality of Life (ATAQ) in IPF Symptoms Questionnaire

The ATAQ-IPF Symptoms Questionnaire is an IPF specific, self-administered questionnaire that assesses the subject's disease symptoms across three domains (physical activity, cough, and energy level) and a set of questions pertaining to oxygen use. Items are assessed using a Likert scale with a 24-hr recall period.

5.5.5.4.2. A Tool to Assess Quality of Life (ATAQ) in IPF Impacts Questionnaire

The ATAQ-IPF Impact Questionnaire is an IPF specific, self-administered questionnaire that assesses how IPF affects the subjects' quality of life. Items are assessed using a Likert scale with a one week recall period.

5.5.5.5. Visual Analog Scale (VAS) for Cough Severity

Cough will be assessed using a VAS in which the subject will indicate the severity of their cough by drawing a mark on a 100 mm scale, which ranges from 0 - "no cough" to 100 mm - "worst cough severity". A paper scale will be provided to sites prior to subject enrollment.

5.5.5.6. End of Study Questionnaire

The End of Study Questionnaire is an 8-item survey to evaluate the subjects' experience while on the study including symptoms, changes in oxygen saturation and use. This is a self-administered survey to be completed during the Day 58 visit. The survey is to be completed by subjects enrolled under Part B of the trial. A paper End of Study Questionnaire will be provided to the sites prior to subject enrollment in Part B. Subject responses will be entered in the eCRF by the site. At completion of the study the paper questionnaires will be returned to the Sponsor.

5.6. Pharmacokinetic Samples

Plasma and whole blood concentrations of GBT440 will be measured using validated LCMS methods. Instructions for sample collection, processing and shipment are described in a separate lab manual. Up to nine PK samples will be collected at the following times (also refer to the Schedule of Assessments, [Appendix A](#)):

	During Treatment Period	
	Pre-dose	2 hrs ± 15 min post -dose
Day 1 (Visit 2)	X	X
Day 2 (Visit 3)	X*	
Day 8 (Visit 4)	X	
Day 15 (Visit 5)	X	
Day 28 (Visit 6)	X	X
	During Follow-Up Period	
Day 45 (Visit 8)		X
Day 58 (Visit 9)		X

* On Day 2 the PK sample should be drawn 24 hours (± 2 hours) after the Day 1 dose and prior to receiving the Day 2 dose.

6. EARLY DISCONTINUATION OF STUDY OR INDIVIDUAL SUBJECTS

6.1. Early Discontinuation of the Study and/or Site

The Sponsor has the right to terminate this study at any time. Reasons for terminating the study may include, but are not limited to:

- Incidence or severity of adverse events in this or other studies indicating a potential health hazard to subjects.
- Unsatisfactory subject recruitment e.g. excessively slow
- Poor protocol adherence
- Incomplete or inaccurate data recording
- Poor compliance with the International Conference on Harmonisation (ICH) guidelines for Good Clinical Practice (GCP)

In any instance of early discontinuation of the study, the Sponsor will notify, in writing, the investigators, regulatory authorities and ethics committees, and will specify the reason(s) for termination.

6.2. Early Discontinuation of Individual subjects

Reasons for subject withdrawal from the study may include but are not limited to any of the following reasons:

- Subject withdrawal of consent
- Discretion of the Investigator, if it is deemed not safe, or in the subject's best interest, to continue
- SMC recommendation
- Subject is lost to follow-up

The date and reason for discontinuation should be documented in the eCRF.

Subjects who discontinue the study should return to the site to complete the Visit 8 (Day 45) assessments within 2 weeks (± 7 days) from the date of discontinuation.

6.3. Study Treatment Discontinuation

Subjects should discontinue study drug for any of the following reasons:

- Malignancy: not including local and non-serious basal or squamous cell skin cancer
- Pregnancy
- Anaphylaxis, anaphylactoid or serious hypersensitivity reaction
- Use of any medication (refer to [Section 8.5](#)), intended to chronically treat IPF, other than those documented at screening
- Adverse event which in the opinion of the investigator precludes the subject from safely continuing in the study
- Pulmonary rehabilitation started at any time from screening until the end of the study
- Subject is noncompliant with study requirements

The date and reason for discontinuation should be documented in the eCRF.

Subjects who discontinue study drug should continue in the study to complete all scheduled assessments.

Those subjects who are unwilling or unable to complete all remaining study assessments, should return to the study site 2 weeks (+ 7 days) after the last dose of study drug to complete the Visit 8 (Day 45) assessments.

In this way all subjects will be assessed at least 5 half-lives after the last dose of study drug

7. STUDY DRUG AND ACCOUNTABILITY

7.1. Study Drug

7.1.1. Physical Description

GBT440 is synthetic small molecule bearing the chemical name 2-hydroxy-6-((2-(1-isopropyl-1H-pyrazol-5-yl) pyridin-3-yl) methoxy) benzaldehyde. The chemical formula is $C_{19}H_{19}N_3O_3$ and the molecular weight is 337.38.

7.1.2. Formulation

GBT440 Capsules: GBT440 will be provided as 300 mg capsules which contain GBT440 drug substance in Swedish orange, opaque, size 0, hypromellose capsules along with several formulation excipients including hypromellose, microcrystalline cellulose, lactose monohydrate, croscarmellose sodium and magnesium stearate. All the excipients used for the formulation are FDA IID (Inactive Ingredients Database) listed.

Placebo Capsules: The placebo capsules contain microcrystalline cellulose in Swedish orange, opaque, size 0, hypromellose capsules. All the excipients used for the formulation are FDA IID (Inactive Ingredients Database) listed. The placebo capsules do not contain any GBT440 drug substance.

7.1.3. Packaging and Labeling

GBT440 and placebo capsules will be supplied to the site in 100 mL high-density polyethylene (HDPE) bottles induction sealed with child-resistant polypropylene (PP) screw caps bottles of 30 capsules.

An unblinded study pharmacist will prepare daily doses of study drug dispensed into 30 mL high-density polyethylene (HDPE) bottles with child-resistant polypropylene (PP) screw caps. Packaging and labeling of each bottle and its contents are specific to each subject in the study and is based on the treatment group assignment at randomization.

Each 30 mL bottle (or dose) is packaged individually with 3 capsules of active or placebo or both specific to each subject's assigned treatment group.

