8. DOSAGE AND TREATMENT ADMINISTRATION

8.1. Treatment Regimen

GBT440 and placebo will be administered orally each day for 28 days. GBT440 will be administered as 300 mg capsules. Placebo will be provided as capsules matching the GBT440 capsules. Subjects randomized to the following treatment groups will receive:

Part A:

- GBT440 900 mg: 3 GBT440 300 mg capsules.
- GBT440 600 mg: 2 GBT440 300 mg capsules and 1 placebo capsule.
- Placebo: 3 placebo capsules.

Part B:

- GBT440 1500 mg: 5 GBT440 300 mg capsules
- GBT440 600 mg: 2 GBT440 300 mg capsules and 3 placebo capsule.
- Placebo: 5 placebo capsules.

Instructions for Administration of Study Drug:

- Self-administered by subject in the morning
 - except on study visit days when the subject must not take study drug. It will be administered at the site after completion of scheduled assessments.
- May be taken with or without food
- May be taken with water or other non-alcoholic beverage

Subjects must be instructed not to take study drug the day of their scheduled visits (refer to [Appendix A](#)). Study drug will be administered at the site on these days, after completion of all the assessments scheduled for that visit.

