8.2. Study Drug Dispensing

Study drug will be dispensed to subjects on study Days 2, 8 and 15 as indicated in the schedule of assessments (refer to [Appendix A](#)). Each daily dose will be dispensed into separate containers and provided to the subject at the study site.

If a dose reduction is required subjects must return to the study site for study drug to be re-dispensed. Subjects must return any remaining study drug and all study drug containers to the site where they will be destroyed as instructed by the Sponsor.

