- k Performed for all female patients who are not post-menopausal or surgically sterile
- l If a urine pregnancy test is positive the result must be confirmed with a serum pregnancy test
- m PK blood samples during the treatment period should be collected on Days 1 and 28: Pre-dose and 2 hours post dose (+/- 15 minutes); Day 2: 24 hours (+/-2 hours) after the Day 1 dose *and* prior to receiving the Day 2 dose; Days 8 and 15: Pre-dose only.
- n Instructions for per-protocol performance of the 6-minute walk (and Borg dyspnea scale) and cardio-pulmonary exercise tests are provided in the procedure manual. Note: The baseline 6MWT performed during screening must be performed within 7 days of the Day 1 visit.
- o An unblinded study pharmacist will prepare daily doses of study drug, dispensed into 30 mL high-density polyethylene (HDPE) bottles. Each bottle (or dose) is packaged individually with 3 capsules of active or placebo or both specific to each subject's assigned treatment group. Subjects who have their dose modified during the study must return to the site to have the modified dose of study drug dispensed by the unblinded pharmacist.
- p Subjects should not administer study drug on the morning of these study visits. Study drug will be administered by the study staff after completion of all pre-dose assessments.
- q The SGRQ, ATAQ and UCSD questionnaires and cough VAS should be self-administered by the subject, using the paper forms provided by the Sponsor prior to all other non-PRO assessments and before the patient receives any disease-status information during that assessment. ATAQ questionnaires should be administered to subjects enrolled in Part B of the study.
- r The End of Study Questionnaire should be administered to subjects enrolled in Part B of the study.

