- ^m PK blood samples during the treatment period should be collected on Days 1 and 28: pre-dose, and 2 hours post dose (+/- 15 minutes); Day 2: 24 hours (+/- 2 hours) after the Day-1 dose *and* prior to receiving the Day-2 dose; Days 8 & 15: pre-dose only. Also see Protocol Section 5.6.
- ⁿ Instructions for per-protocol performance of the 6-minute walk (and Borg dyspnea scale) and cardio-pulmonary exercise tests are provided in the procedure manual. Note: The baseline 6MWT performed during screening must be performed within 7 days of the Day-1 visit.
- ^o An unblinded study pharmacist will prepare daily doses of study drug, dispensed into 30 mL high-density polyethylene (HDPE) bottles. Each bottle (or dose) is packaged individually with 3 capsules of active or placebo or both specific to each subject’s assigned treatment group. Subjects who have their dose modified during the study must return to the site to have the modified dose of study drug dispensed by the unblinded pharmacist.
- ^p Subjects should not administer study drug on the morning of these study visits. Study drug will be administered by the study staff after completion of all pre-dose assessments.
- ^q The SGRQ, ATAQ, and UCSD questionnaires and cough VAS should be self-administered by the subject, using the paper forms provided by the Sponsor prior to all other non-PRO assessments and before the patient receives any disease-status information during that assessment. ATAQ questionnaires should be administered to subjects enrolled in Part b of the study.
- ^r The End of Study Questionnaire should be administered to subjects enrolled in Part B of the study.

6. Study Treatments

The study drug is GBT440 300 mg capsules or placebo.

Subjects randomized to the following treatment groups in Part A will receive:

- GBT440 900 mg -- 3 GBT440 300 mg capsules
- GBT440 600 mg -- 2 GBT440 300 mg capsules and 1 placebo capsule.
- Placebo -- 3 placebo capsules.

Subjects randomized to the following treatment groups in Part B will receive:

- GBT440 1500 mg -- 5 GBT440 300 mg capsules
- GBT440 600 mg -- 2 GBT440 300 mg capsules and 3 placebo capsules.
- Placebo -- 5 placebo capsules.

Study drug is to be dosed orally once daily for a total of 28 days.

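### The 3-capsule bottle text and the three-times-daily option were not updated for Part B, where every arm takes 5 capsules a day

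*Protocol*

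**What the plan says.** **Bottle contents.** Protocol 7.1.3 states: "Each 30 mL bottle (or dose) is packaged individually with 3 capsules of active or placebo or both". Note o to the schedule in protocol Appendix A repeats it ("Each bottle (or dose) is packaged individually with 3 capsules of active or placebo or both"), and note o in SAP 5.1 does the same. None of the three restricts the count to Part A. Protocol 8.2 adds: "Each daily dose will be dispensed into separate containers and provided to the subject at the study site". A bottle is therefore one day's dose. Protocol 7.1.3 also says that what goes into each bottle "is based on the treatment group assignment at randomization".

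**Part B regimen.** Protocol 8.1 lists "GBT440 1500 mg: 5 GBT440 300 mg capsules" for the top dose. SAP section 6 gives the lower active arm "2 GBT440 300 mg capsules and 3 placebo capsules". Placebo subjects take 5 placebo capsules. Protocol 3.1 and SAP section 4 agree.

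**Dose adjustment.** Protocol 8.3.1 and SAP 6.2 list two options as separate bullets: moving to single capsules taken three times daily, and lowering the daily total. Reductions go down by one active capsule at a time, with a second step allowed. In the same paragraph as the reduction rule, both documents say that subjects stay on 3 capsules daily in Part A and 5 in Part B.

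**The concern.** Three capsules is the Part A count. It was carried unchanged into text that now governs both parts. Neighbouring text was revised for Part B: notes q and r in Appendix A refer to it, and so does the 5-capsule sentence in protocol 8.3.1. The bottle sentence was missed in three places and the frequency bullet in two.

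These are working instructions for the unblinded pharmacist and the investigator. Safety and tolerability are the primary objective, and only 9 subjects are planned at 1500 mg, so the dose each of them takes should not depend on which sentence a site follows.

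The planned exposure summaries might not reveal a discrepancy. SAP 14.1 counts dose reductions, and a change labelled as one of frequency might not be recorded as one. SAP 14.2 and 14.3 measure exposure and compliance in days dosed, so a subject taking 3 of 5 capsules every day would still show full compliance.

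**Working it through.** **Inputs.** Capsule strength is 300 mg. Capsules per arm come from protocol 8.1 and SAP section 6, bottle count from protocol 7.1.3 and note o in both schedules, and reduction steps from protocol 8.3.1 and SAP 6.2.

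**1. Capsules per day by arm** (active + placebo; dose = active × 300 mg)

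| Part | Arm | Active + placebo | Capsules | Dose |
|---|---|---|---|---|
| A | 900 mg | 3 + 0 | 3 | 900 mg |
| A | 600 mg | 2 + 1 | 3 | 600 mg |
| A | Placebo | 0 + 3 | 3 | 0 mg |
| B | 1500 mg | 5 + 0 | 5 | 1500 mg |
| B | 600 mg | 2 + 3 | 5 | 600 mg |
| B | Placebo | 0 + 5 | 5 | 0 mg |

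The stated bottle count of 3 is reproduced for every Part A arm and for no Part B arm.

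**2. Bottle text applied to Part B.** A 3-capsule bottle holds 3/5 = 60% of the daily count. In the 1500 mg arm it supplies at most 3 × 300 = 900 mg, a shortfall of 1 − 900/1500 = 40%. Supplying several bottles a day does not reconcile the text: it equates a bottle with a dose, and bottles of 3 cannot total 5.

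**3. Three-times-daily option in Part A.** 3 × 1 = 3 capsules a day. The 900 mg arm keeps 3 × 300 = 900 mg, and the 600 mg arm keeps 2 × 300 = 600 mg plus one placebo. Only the timing changes, as the separate bullet implies.

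**4. Three-times-daily option in Part B.** Again 3 capsules a day, against the 5 that the same section says Part B subjects continue to take. There are two ways to read that 5-capsule sentence:

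- *It covers every adjustment.* Then the option (3 capsules) and the sentence (5 capsules) contradict each other, and the option cannot be used as written.
- *It covers only dose reductions*, the paragraph in which it stands. Then the option gives the 1500 mg arm at most 900 mg.

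**5. Comparison with the permitted reductions, 1500 mg arm.** First step: 1500 − 300 = 1200 mg (20% less). Second step: 1200 − 300 = 900 mg (40% less). On the second reading, one frequency change lands where two reductions would, without being called a reduction.

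**6. A split that works.** 2 + 2 + 1 = 5 capsules over the day, which keeps 1500 mg (5 active) or 600 mg (2 active, 3 placebo).

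**The case against.** The case for leaving this alone is substantial.

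- **The dose is not in doubt.** Protocol 3.1 and 8.1 and SAP sections 4 and 6 state the Part B capsule counts explicitly. Protocol 7.1.3 ties bottle contents to the assigned arm, although its count of 3 stays fixed.
- **Dispensing has checks.** On Days 1, 2, 8, 15 and 28 dosing takes place at the site: "Study drug will be administered by the study staff after completion of all pre-dose assessments". Protocol 7.2 requires sites to account for all supplies. Further detail is left to a pharmacy manual that is not among the documents and may already give the right counts.
- **The frequency option is gated.** Protocol 8.3 asks that the Sponsor's Medical Director be contacted before any dosing change, and 8.3.1 makes the choice one for discussion with that person. The Sponsor is unblinded in Part B, so the arm can be known. Subjects whose dose is modified "must return to the site to have the modified dose of study drug dispensed by the unblinded pharmacist".
- **The 5-capsule sentence is there.** It shows that 8.3.1 was partly updated and what was intended.

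All of this stands and limits the consequence. It does not make the sentences right: three bottle statements remain incorrect for Part B, and the frequency bullet either contradicts its neighbour or changes the dose.

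A reader might infer that the 1500 mg arm will be under-dosed, or that an investigator choosing the frequency option would necessarily cut the dose by 40%. The documents do not support either, given the checks above; the most they allow is that it could happen if the text were followed literally.

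A reader might also infer that the Part B 600 mg arm could drop to 300 mg or to nothing, because no three-capsule mix is stated. That is speculative. An option listed apart from dose reduction is most naturally read as keeping the daily total, which gives 2 active and 1 placebo, or 600 mg.

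**Conclusion.** The point holds as a minor internal inconsistency from an incomplete Part B amendment.

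- **Bottle text:** wrong as written for all three Part B arms. Read literally, it caps the 1500 mg arm at 900 mg (40% less). That is the size of the textual error, not an expected under-dose.
- **Frequency option:** it either conflicts with the 5-capsule sentence or, if that sentence covers only reductions, could move a 1500 mg subject to at most 900 mg in one step, against 1200 mg after one defined reduction. It would affect single subjects, each 1 of the 9 planned in that arm.

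This rests on two assumptions: that a bottle is one daily dose, as protocol 7.1.3 and 8.2 indicate, and that no unseen document overrides the text. A pharmacy manual with the right counts would remove most of the practical risk but leave the protocol and SAP inconsistent.

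It should not be taken as a calculation error or a flaw in the statistical design. No sample size, endpoint, analysis population or model changes.

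**What to change.** 1. In protocol 7.1.3, protocol Appendix A note o and SAP 5.1 note o, state 3 capsules per bottle for Part A and 5 for Part B.
2. In protocol 8.3.1 and SAP 6.2, either limit the three-times-daily option to Part A, or define a Part B split that keeps all 5 capsules and the assigned daily dose, for example 2+2+1.
3. Check that the pharmacy manual agrees with both.

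The cost is wording: three bottle sentences and one bullet in two places. The protocol changes would go to the IRB/IEC as an amendment under protocol 12.2. No extra subjects, visits or procedures are needed.

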7.1.4. Supply

GBT or their representative will supply the packaged and labeled drug product to the investigational sites. Additional details are provided in the pharmacy manual.

7.1.5. Storage and Handling Procedure

All study medications will be stored at controlled room temperature between 15°C to 25°C protected from light in the storage area of the investigational site pharmacy, which is a secure, temperature controlled, locked environment with restricted access.

No special procedures for the safe handling of GBT440 or placebo are required. The Sponsor will be permitted upon request to audit the supplies, storage, dispensing procedures and records provided that the blind of the study is not compromised.

7.2. Drug Accountability

In accordance with GCP, the Investigational Site will account for all supplies of GBT440 and placebo. Details of receipt, storage, assembly and return will be recorded.

All unused supplies of GBT440 and placebo will either be destroyed by the investigational site or returned to the study Sponsor or designee at the end of the study in accordance with instructions from the Sponsor.

Additional details are provided in the pharmacy manual.

8. DOSAGE AND TREATMENT ADMINISTRATION

8.1. Treatment Regimen

GBT440 and placebo will be administered orally each day for 28 days. GBT440 will be administered as 300 mg capsules. Placebo will be provided as capsules matching the GBT440 capsules. Subjects randomized to the following treatment groups will receive:

Part A:

- GBT440 900 mg: 3 GBT440 300 mg capsules.
- GBT440 600 mg: 2 GBT440 300 mg capsules and 1 placebo capsule.
- Placebo: 3 placebo capsules.

Part B:

- GBT440 1500 mg: 5 GBT440 300 mg capsules
- GBT440 600 mg: 2 GBT440 300 mg capsules and 3 placebo capsule.
- Placebo: 5 placebo capsules.

Instructions for Administration of Study Drug:

- Self-administered by subject in the morning
 - except on study visit days when the subject must not take study drug. It will be administered at the site after completion of scheduled assessments.
- May be taken with or without food
- May be taken with water or other non-alcoholic beverage

Subjects must be instructed not to take study drug the day of their scheduled visits (refer to [Appendix A](#)). Study drug will be administered at the site on these days, after completion of all the assessments scheduled for that visit.

